7.4.5 GVHD

Neither acute or chronic GVHD require reporting to Genentech.

7.4.6 Post-Study Adverse Events

The investigator should expeditiously report any SAE occurring after a patient has completed or discontinued study participation if attributed to prior obinutuzumab exposure. If the investigator should become aware of the development of cancer or a congenital anomaly in a subsequently conceived offspring of a female patient who participated in the study, this should be reported as an SAE.

7.5 Adverse Events of Special Interest (AESIs) for Genentech

AEs of special interest (AESIs) are defined as a potential safety problem, identified as a result of safety monitoring of Obinutuzumab. Adverse events of special interest (AESI) in clinical trials are sent to Genentech within 24 hours, even when they are considered non-serious by the investigator.

The following AESIs must be reported to the Sponsor expeditiously irrespective of regulatory seriousness criteria:

- Tumor Lysis Syndrome (serious and non- serious events)

The following events can be reported as AESI only when considered SERIOUS by the investigator:

- Serious neutropenia
- Serious infection
- Serious Infusion Related Reaction (IRR)

Other selected events can be considered for reporting as AESIs:

• infections (including PML)

- neutropenia (including late onset neutropenia defined as neutrophil count < 1000 cells/mm3, occurring 28 days or more after obinutuzumab treatment has been completed or stopped; prolonged neutropenia defined as neutrophil count < 1000 cells/mm3, which does not resolve after 28 days (without obinutuzumab treatment),
- thrombocytopenia (including acute thrombocytopenia events occurring during and within 24 hours post obinutuzumab infusion)
- Hepatitis B reactivation
- cardiac events
- second malignancies
- GI perforation.

7.6 Serious Adverse Event Reporting to Roche/Genentech

Investigators must report all AESIs and SAEs to Roche/Genentech within the timelines described below. The completed MedWatch/case report (Appendix B) should be faxed/emailed immediately upon completion to Genentech at the following contacts:

All protocol-defined AEs, SAEs, AESIs, Special Situation Reports (including pregnancy reports) and Product Complaints with an AE should be sent to:

[contact]

Email: usds [contact]

All Product Complaints without an AE should be sent to:

Email: [name] [contact]

A cover sheet for faxes to Roche/Genentech is found in Appendix C

A copy of the submitted institutional AESIs, SAEs, Special Situation Reports (including pregnancy reports) and Product Complaints (with or without an AE) should be forwarded to the Overall PI.

Relevant follow-up information should be submitted to Roche/Genentech Drug Safety as soon as it becomes available.

Serious AE reports that are related to obinutuzumab will be transmitted to Roche/Genentech within 15 calendar days of the Awareness Date.

The Principal Investigator will periodically forward listings of non-serious AEs originating from the Study to Roche/Genentech.

In addition to SAEs and pregnancy reports, the following Special Situations Reports should be collected and transmitted to Roche/Genentech even in the absence of an Adverse Event within thirty (30) calendar days:

- Data related to product usage during pregnancy or breastfeeding
- Data related to overdose, abuse, misuse, inadvertent/erroneous administration, medication error or
 occupational exposure, with or without association with an AE/SAE unless otherwise specified in the
 protocol

Product Complaints:

All Product Complaints (with or without an AE) shall be forwarded to Genentech within fifteen (15) calendar days of the awareness date.

A Product Complaint is defined as any written or oral information received from a complainant that alleges

deficiencies related to identity, quality, safety, strength, purity, reliability, durability, effectiveness, or performance of a product after it has been released and distributed to the commercial market or clinical trial.

Investigators should also report events to their IRB as required.

7.6.1 MedWatch 3500A Reporting Guidelines

In addition to completing appropriate patient demographic and suspect medication information, the report should include the following information within the Event Description (item 5) of the MedWatch 3500A form:

• Protocol description (and number, if assigned)

- Description of event, severity, treatment, and outcome if known
- Supportive laboratory results and diagnostics
- Investigator's assessment of the relationship of the to each investigational product and suspect medication

Additional information may be added to a previously submitted report by any of the following methods:

- Adding to the original MedWatch 3500A report and submitting it as follow-up
- Adding supplemental summary information and submitting it as follow-up with the original MedWatch 3500A form
- Summarizing new information and faxing it with a cover letter including patient identifiers (i.e., D.O.B. initial, patient number), protocol description and number, if assigned, brief AE description, and notation that additional or follow-up information is being submitted (The patient identifiers are important so that the new information is added to the correct initial report)

Occasionally Roche/Genentech may contact the reporter for additional information, clarification, or current status of the patient for whom and AE was reported. For questions regarding SAE reporting, you may contact the Roche/Genentech Drug Safety representative noted above or the MSL assigned to the study. Relevant follow-up information should be submitted to Roche/Genentech Drug Safety as soon as it becomes available and/or upon request.

MedWatch 3500A form is available at http://www.fda.gov/AboutFDA/ReportsManualsForms/Forms/default.htm

7.7 Expedited Reporting to Hospital Risk Management

Participating investigators will report to their local Risk Management office any participant safety reports or sentinel events that require reporting according to institutional policy.

8. PHARMACEUTICAL INFORMATION

A list of the adverse events and potential risks associated with the investigational agent administered in this study can be found in Section 7.1.

8.1 Obinutuzumab

8.1.1 Description

Obinutuzumab is a humanized and glycoengineered type II anti-CD20 monoclonal antibody of the IgG1 subclass. It recognizes a specific epitope of the CD20 molecule found on B-cells. The molecular mass of the antibody is approximately 150 kDa.

An antibody-producing cell line was established from the CHO K1 cell line.

INN: Obinutuzumab

Code Number: Drug substance: RO5072759

Drug product: Ro 5072759/F06-01 (1000 mg/vial)

Chemical Name: Humanized glycoengineered type II anti-CD20 monoclonal

antibody

Other Names: GAZYVA®, GAZYVARO™, huMAb<CD20>, GA101

Chemical Structure: H2L2 polypeptide structure consisting of two light chains and two

heavy chains held together by disulfide bonds.

Molecular Weight: Approximately 150 kDa

Description: The drug substance is a clear, colorless to slightly brownish liquid.

The drug product is a colorless to slightly brownish liquid

concentrate.

8.1.2 Form

Obinutuzumab is provided as a single 1000 mg dose liquid concentrate with a strength of 25 mg/mL. It is supplied in 50 mL glass vials containing 40 mL of the 25 mg/mL liquid concentrate. In addition to the antibody, the liquid also contains histidine/histidine-HCl, trehalose, poloxamer 188 and HPW. HPW meets the specified limits for highly purified water according to Ph.Eur. and for WFI according to USP.

8.1.3 Storage and Stability

The recommended storage conditions for obinutuzumab drug product are between 2°C and 8°C, protected from light.

For microbiological stability, the diluted obinutuzumab infusion solution should be used immediately.

8.1.4 Compatibility

Do not mix obinutuzumab with other drugs.

No incompatibilities between obinutuzumab and polyvinylchloride (PVC) or non-PVC polyolefin bags and administration sets have been observed.

8.1.5 Handling

Qualified personnel, familiar with procedures that minimize undue exposure to themselves and the environment, should undertake the preparation, handling, and safe disposal of the chemotherapeutic agent in a self-contained and protective environment.

8.1.6 Availability

Obinutuzumab will be distributed to the Study Sites directly from Genentech, Inc.

8.1.7 Preparation

Prepare the solution for infusion, using aseptic technique, as follows:

Inspect visually for any particulate matter and discoloration prior to administration.

Dilute into a 0.9% sodium chloride PVC or non-PVC polyolefin infusion bag. Do not use other diluents such as dextrose (5%).

Remove 20 ml overfill from 0.9% sodium chloride 250 ml bag. Remove an additional 40 ml from the 0.9% sodium chloride 250 ml bag.

Withdraw 40 mL (1000 mg) of obinutuzumab and inject into the 0.9% sodium chloride bag.

Mix diluted solution by gentle inversion. Do not shake.

Total volume for administration is 250 ml.

Final concentration is 4 mg/ml.

The prepared infusion solution should be used immediately or may be stored at 2 to 8 degrees C (36 to 46 degrees F) for up to 24 hours.

8.1.8 Administration

Initial Dose

Research subjects should be premedicated with Acetaminophen (650 - 1000 mg oral) and Diphenhydramine (25-50 mg intravenous).

Obinutuzumab is administered initially at 50 mg/h. In the absence of infusional reactions, the rate can be increased in increments of 50 mg/h every 30 minutes to a maximum of 400 mg/h. With this schedule, a 1000 mg dose of Obinutuzumab will be infused over 4.25 hours.

Second and Subsequent Doses

Research subjects should be premedicated with Acetaminophen (650 - 1000 mg oral) and Diphenhydramine (25-50 mg intravenous).

In the absence of severe infusional reactions with the initial dose, Obinutuzumab can be administered initially at 100 mg/h. In the absence of infusional reactions, the rate can be increased in increments of 100 mg/h every 30 minutes to a maximum of 400 mg/h. With this schedule, a 1000 mg dose of Obinutuzumab will be infused over 3.25 hours.

Doses and schedules are adapted from Phase I and Phase II studies in non-CLL patient populations.²¹⁻²⁴

Placebo will administered at the same rate with the same pre-medications as obinutuzumab.

8.1.9 Ordering

Obinutuzumab will be ordered directly from Genentech, Inc by each study site.

8.1.10 Accountability

Each research Pharmacy will maintain a careful record of the inventory and disposition of the agent using locally approved drug accountability forms.

8.1.11 Reconciliation

The Sponsor agrees to conduct reconciliation for the product. Roche/Genentech and the Sponsor will agree to the reconciliation periodicity and format, but agree at minimum to exchange quarterly (no less frequently than monthly) line listings of cases received by the other party. If discrepancies are identified, the Sponsor and Roche/Genentech will cooperate in resolving the discrepancies. The responsible individuals for each party shall handle the matter on a case-by-case basis until satisfactory resolution. The sponsor shall receive reconciliation guidance documents within the 'Activation Package'.

8.1.12 Destruction and Return

All unused obinutuzumab will be destroyed and disposed by the Research Pharmacy at the conclusion of the trial according to local pharmacy practices.

8.2 Placebo

Placebo compound will be prepared by each research pharmacy to physically resemble the active treatment agent. Placebo will be 0.9% sodium chloride 250 ml bag. Remove 20 ml overfill from the bag for a total volume 250 ml

9. BIOMARKER, CORRELATIVE, AND SPECIAL STUDIES

Approximately 40-50 subjects enrolled in this clinical trial will be F→M subjects, 50% of who will receive obinutuzumab prophylaxis. Comparing obinutuzumab and placebo recipients, we will examine whether effective prevention of alloreactive B cells development, H-Y antibody development or a reduction in H-Y antibody titers correlate with prevention of clinical cGVHD or subsequent severity of cGVHD. We will determine if H-Y antibodies that predate the initial administration of obinutuzumab are predictive of eventual cGVHD development. This latter observation will inform future studies, which may examine earlier administration of obinutuzumab after HCT. All subjects will undergo routine immunophenotyping to monitor the kinetics of BAFF and B cell recovery after obinutuzumab/placebo administration.

Samples will be collected in conjunction with study visits, and no additional study visits are required to fulfill the correlative study objectives.

Peripheral Blood Samples:

Peripheral blood samples will be collected at 3 months, 3.5 months, 6 months, 9 months, 12 months, 18 months, and 24 months from the time of transplantation.

The volume and frequency will not exceed the recommended blood amounts. (It will not exceed 200 mL/day and a maximum of 275 mL in a four week period).

Processing and Shipping Samples:

This is optional for non-DFHCC centers.

Samples will be processed as follows.

- 1. Blood from the first tube will be used for immune cell subset analysis by flow cytometry.
- 2. The remainder of the tube will be used for DNA extraction.
- 3. If the non-DFHCC centers prefer to process the samples on-site, the 1st tube of would be frozen as whole blood, and the DNA would later be extracted at Dana-Farber.
- 4. The 2nd tube will be centrifuged, and 4 mls of plasma will be frozen in vials of 1 ml each.
- 5. The remaining blood from the 2nd tube and the 3rd tube will be used for Ficoll-Paque density gradient sedimentation, and the isolated mononuclear cells frozen in aliquots of approximately 20 million cells per 1ml-vial in 10% DMSO.
- 6. All samples should be stored in 1.8cc Nunc vials.
- 7. Frozen plasma should be stored at -70° C to -20° C. Cryopreserved mononuclear cells should be stored in vapor phase liquid nitrogen.
- 8. Samples older than 48 hours are too old to bank, except for DNA.

10. STUDY CALENDAR

	Month											
	Pre- transplant	Screening ²	3^3	3.5	6^3	6.5	93	9.5	12 ³	12.5	1810	2410
Obinutuzumab	1		\otimes		\otimes		\otimes		\otimes			
Placebo			\otimes		\otimes		\otimes		\otimes			
Medical		•	•	•	•		•		•		•	•
History												
Physical		•	•	•	•		•		•		•	•
Examination												
CBC with		•	•	•4	•	•4	•	•4	•	•4	•	•
differential												
Pulmonary Function Test		•							•			•
Pregnancy		•										
Test												
Informed Consent		•										
Chimerism analysis ⁵		•			•		•		•		•	•
Tumor Staging		•										
Immunology ⁶			•	•	•		•		•		•	•
Chronic GVHD Assessment ⁹					•		•		•		•	•
Toxicity			•	•	•		•		•		•	•
Assessment												
Infectious	•											
Disease Testing ⁷												
Patient Survey ⁸					•		•		•		•	•

¹As measured from the time of transplantation.

²Screening can begin 60 days from transplantation

³The administration of Obinutuzumab at month 3, 6, 9 and 12 can be +/- 10 days. Similarly, the required follow-up after the first administration of Obinutuzumab occurs +/-4 days 14 days after the administration of Obinutuzumab.

⁴CBC after obinutuzumab should be 14 +/-4 days from the administration of obinutuzumab. CBCs can be performed at local providers, except after the first infusion.

⁵Chimerism studies are required at screening for only subjects who have undergone non-myeolablative transplantation. Chimerism analysis will be performed by single locus microsatellite DNA probes. Total and T cell chimerism measurements should be performed at all evaluation timepoints for all patients regardless of

conditioning regimen.

⁶Quantitative immunoglobulin measurement; Lymphocyte subset analysis for B cells, T cells; ELISA for minor histocompatibility antigens DBY, DBX under the appropriate clinical conditions (sex-mismatch); Plasma banking, and storage of additional mononuclear cells. See Section 9 for additional details.

⁷Testing done in the pre-transplant setting is sufficient to rule out active Hepatitis A, Hepatitis B, Hepatitis C, and HIV infection.

⁸Patient GVHD will be administered to patients during the Month 6, 9, 12, 18, and 24 appointments. Continue to administer at follow-up visits even if patient has been taken off treatment. Survey is located in Appendix E.

⁹Provider cGVHD survey administered at the month 6, 9, 12, 18, and 24 appointments.

¹⁰There is a +/- 21 day window for month 18 and month 24 appointments.

11. DATA REPORTING / REGULATORY REQUIREMENTS

Adverse event lists, guidelines, and instructions for AE reporting can be found in Section 7.

11.1 Data Reporting

11.1.1 Method

The ODQ/CTRIO will collect, manage, and perform quality checks on the data for this study.

11.1.2 Responsibility for Data Submission

Investigative sites within DF/HCC or DF/PCC are responsible for submitting data and/or data forms to the ODQ/CTRIO according to the schedule set by the ODQ/CTRIO.

11.2 Data Safety Monitoring

The DF/HCC Data and Safety Monitoring Board (DSMB) will review and monitor study progress, toxicity, safety and other data from this study. The board is chaired by a medical oncologist from outside of DF/HCC and has external and internal representation. Information that raises any questions about participant safety or protocol performance will be addressed by the Overall PI, statistician and study team. Should any major concerns arise, the DSMB will offer recommendations regarding whether or not to suspend the study.

The DSMB will meet twice a year to review accrual, toxicity, response and reporting information. Information to be provided to the DSMB may include: participant accrual; treatment regimen information; adverse events and serious adverse events reported by category; summary of any deaths on study; audit results; and a summary provided by the study team. Other information (e.g. scans, laboratory values) will be provided upon request.

11.3 Multicenter Guidelines

This protocol will adhere to the policies and requirements of the DF/HCC Multi-Center Data and Safety Monitoring Plan. The specific responsibilities of the Overall PI, Coordinating Center, and Participating Institutions and the procedures for auditing are presented in Appendix D.

• The Overall PI/Coordinating Center is responsible for distributing all IND Action Letters or

Safety Reports to all participating institutions for submission to their individual IRBs for action as required.

• Mechanisms will be in place to ensure quality assurance, protocol compliance, and adverse event reporting at each site.

• Except in very unusual circumstances, each participating institution will order the study agent(s) directly from supplier. A participating site may order the agent(s) only after the initial IRB approval for the site has been forwarded to the Coordinating Center.

12. STATISTICAL CONSIDERATIONS

This is a prospective, multicenter, randomized phase II trial of prophylactic obinutuzumab vs. placebo for prevention of cGVHD after HCT. The primary objective is to determine the effect of obinutuzumab prophylaxis on the incidence of corticosteroid-requiring cGVHD after allogeneic HCT. A single dose of obinutuzumab or placebo will be administered prophylactically at 3, 6, 9, and 12 months after HCT.

12.1 Study Design/Endpoints

This is a randomized, Phase II trial. The primary objective is to determine the rate of corticosteroid-requiring cGVHD when obinutuzumab is used as cGVHD prophylaxis.

The primary endpoint of this phase II trial is the rate of corticosteroid-requiring cGVHD at one year from HCT.

Secondary objectives are to determine the overall cGVHD rate after HCT, NIH moderate-severe cGVHD rate after HCT, cumulative incidence of non-relapse mortality and relapse, adverse hematologic events and infections, immunosuppression-free survival (IFS) at 1 and 2 years from transplantation, progression-free and overall survival at 1 and 2 years from transplantation, and immunologic correlates of B cell depletion. IFS is defined as time from randomization to relapse, institution of systemic immune suppression, or death, whichever occurs first.

12.2 Sample Size, Accrual Rate and Study Duration

The sample size is 200 eligible patients, based on event rates from DFCI 05-377. In this study, 65 patients who received rituximab as cGVHD prophylaxis were compared to a contemporaneous control group and the 1-year corticosteroid-requiring cGVHD rate was 21% in the rituximab group and 38% in the control group. Based on this information, we assume that the 1-year corticosteroid-requiring cGVHD rate will be 38% in the control group and hypothesize that there will be at least a 45% reduction in the obinutuzumab group to a 1-year corticosteroid-requiring cGVHD rate of 21%. With 200 eligible patients, the study will have 80% power to detect a 45% reduction in the obinutuzumab arm using a two-sided test at a significance level of 0.1. This power calculation is based on Fisher's exact test.

Accrual from 3 participating clinical sites (DFCI, MGH, Stanford) is projected to be approximately 100 patients/year, given competing trials and relapse or death prior to 3 months from HCT. Based on this projection, we anticipate that the study will complete its accrual in 2 years.

Patients who initially join the study but are later deemed ineligible due to exclusion criteria 3.2.6 will not be counted toward the overall accrual goal.

All surviving patients will be followed at least for 1 year after HCT for the evaluation of the primary endpoint

Special attention will be paid to the recruitment of women and minorites per NIH guidelines.

12.3 Randomization and Stratification Factors

Randomization will be 1:1, stratified by center, conditioning intensity (myeloablative vs. reduced intensity) and donor type (matched related vs. matched unrelated) using permuted block algorithm within strata.

QACT will notify the research pharmacy of the randomization status of the patient by fax and via email ([contact]). The remainder of the study team will be blinded to which arm the patient will receive.

12.4 Blinding

Blinding will be performed at the level of the Research Pharmacy. Obinutuzumab or placebo will be issued from the Research Pharmacy without identifying labels to prevent unblinding at the bedside.

The research pharmacy will not be blinded. Unblinding will occur when knowledge of the treatment is essential for the emergency management of adverse events. Unblinding may also occur at the request of the Principal Investigator when all patients have come off study treatment. In case of an emergency, the treating physician or study investigator has the sole responsibility for determining if unblinding of a patient's treatment assignment is warranted for medical management of the event. In these events the primary and backup unblinded study members will be the Clinical Research Manager [name], and Regulatory Coordinator [name], and these members will not otherwise be accessing patient data.

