5.3 Treatment Regimen

Obinutuzumab or placebo will be administered at a dose of 1000 mg, intravenously, at 3, 6, 9 and 12 months from transplantation. The first dose is administered at day +90 (+/- 10 days), followed by doses at days +180 (+/- 10 days), 270 (+/- 10 days) and +365 (+/- 10 days).

Premedication with histamine blockers and acetaminophen will be provided (see Section 5.5 below), but corticosteroids at the time of obinutuzumab infusion are not permitted. Placebo will be administered with the same premedications and precautions.

No dose modifications are permitted, although doses may be skipped based on unresolved toxicity (see Section 6: Dosing Delays/Dose Modifications). If a dose is missed, the investigator may choose to continue with protocol-specified treatments within the next dosing time period.

5.4 Pre-Treatment Criteria for Doses 1, 2, 3 and 4

There are no criteria for treatment at dose 1. Dose 1 will be administered at the discretion of the provider.

Criteria for treatment at doses 2, 3 and 4 are:

 $\begin{array}{lll} - & WBC & & \geq 2,500/\mu L \\ - & Absolute \ Neutrophil \ Count & \geq 1,000/\mu L \\ - & Platelets & \geq 50,000/\mu L \end{array}$

The occurrence of acute GVHD prior to doses 2, 3, 4 is allowed as long as all GVHD symptoms are resolved to Gr 0 for hepatic and gastrointestinal disease and Gr I for cutaneous disease, per section 3.2.43.2.4

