5.9 Criteria for Taking a Participant Off Protocol Therapy

The following are criteria for removing a participant from active study:

- The development of steroid-requiring cGVHD
- Malignant disease progression
- Intercurrent illness that prevents further administration of treatment
- Unacceptable adverse event(s)
- Participant demonstrates an inability or unwillingness to comply with the treatment regimen
- Participant decides to withdraw from the protocol therapy
- General or specific changes in the participant's condition render the participant unacceptable for further treatment in the judgment of the treating investigator

Participants will be removed from the protocol therapy when any of these criteria apply. The reason for removal from protocol therapy, and the date the participant was removed, must be documented in the case report form (CRF). Patients with steroid-requiring cGVHD, unacceptable AEs or intercurrent illness preventing further drug administration who come off treatment should continue to have laboratory studies and clinical assessments performed at the appropriate timepoints. Patients with malignant disease progression do not require laboratory or clinical follow-up. Alternative care options will be discussed with the participant.

An ODQ/CTRIO Treatment Ended/Off Study Form will be filled out when a participant is removed from protocol therapy. This form can be found on the ODQ/CTRIO website or obtained from the ODQ/CTRIO registration staff.

In the event of unusual or life-threatening complications, treating investigators must immediately notify the Overall PI, [name] at [contact] [name].

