5.10 Duration of Follow Up

Research subjects will be followed until 2 years from the time of transplantation, or until death, whichever occurs first. Participants removed from protocol therapy for unacceptable adverse events will be followed closely until resolution or stabilization of the adverse event, and then until 2 years from the time of transplantation, or until death, whichever occurs first. Participants who withdraw consent will be followed until that time.

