12.5 Interim Monitoring Plan

The study will be monitored using standard procedures and processes by an independent Data and Safety Monitoring Board (DSMB) of the Dana-Farber Harvard Cancer Center (DF/HCC).

Monitoring of key safety endpoints (relapse, grade 3 or higher treatment related toxicity, grade III-IV acute GVHD after study enrollment) will be conducted in accordance with the DF/HCC DSMB meeting. Since a concern for excess relapse exists, even though our preliminary studies do not support this, we will compare the relapse rate along with other key safety endpoints between two arms at each interim analysis. If, at any interim analysis, this difference is significant at the two-sided level of 0.05, this would trigger a consultation with the DF/HCC DSMB for additional review of early stopping. However, this will not be a formal stopping rule that would mandate automatic closure of study enrollment.

Interim analyses for efficacy will be performed every six months in conjunction with semi-annual DF/HCC DSMB meeting, beginning at the 25% information time, which is anticipated to occur approximately 1.5 years after the start of the trial. The interim results will be reported to the DF/HCC DSMB. However, these interim analyses will not have an effect in terms of stopping accrual to the study and terminate the study early in favor of alternative (superiority) or null hypothesis (futility). This is because i) due to a small sample size at the first interim analysis, stopping early for futility would result in substantially wide confidence intervals, larger Type II error, and thus leading to greater uncertainty about the magnitude of the steroid requiring cGVHD difference, ii) by the time of the second interim analysis, the study is anticipated to complete accrual, iii) even if the steroid requiring cGVHD difference is not as large as targeted, investigators are interested in learning the magnitude of the difference for further investigation, iv) stopping early for superiority would provide less safety data than planned and potential difficulty with the efficacy analysis and its interpretation.

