Overall GVHD Severity (Opinion of the evaluator)	□ No GV	THD Mild	☐ Moderate	☐ Severe	
Photographic Range of M	, ,				
1 (Worst) 2 3 4 5 6 7 (Normal) Shoulder 1 (Worst) 2 3 4 5 6 7 (Normal)					
	Elbow	EFF			
	Wrist/finger 1.00cm	3 4 5	6 7 (Normal)		
	Ankle	2 3 4(Normal)			

- † Skin scoring should use both percentage of BSA involved by disease signs and the cutaneous features scales. When a discrepancy exists between the percentage of total body surface (BSA) score and the skin feature score, OR if superficial sclerotic features are present (Score 2), but there is impaired mobility or ulceration (Score 3), the higher level should be used for the final skin scoring.
- * Weight loss within 3 months.
- **Lung scoring should be performed using both the symptoms and FEV1 scores whenever possible. FEV1 should be used in the final lung scoring where there is discrepancy between symptoms and FEV1 scores.
 Abbreviations: ECOG (Eastern Cooperative Oncology Group), KPS (Karnofsky Performance Status), LPS (Lansky Performance Status); BSA (body surface area); ADL (activities of daily living); LFTs (liver function tests); AP

(alkaline phosphatase); ALT (alanine aminotransferase); ULN (normal upper limit). ‡ To be completed by specialist or trained medical providers (see Supplemental Figure).

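### Section 12.4 allows treatment codes to be released once treatment ends, when at planned accrual about half the patients would not yet have reached month 24

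*Combined protocol and SAP*

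**What the plan says.** Section 12.3 sets up the blind: the research pharmacy is told the allocation, and "The remainder of the study team will be blinded to which arm the patient will receive". It gives no date on which this ends. Section 12.4 provides for emergency unblinding and then adds: "Unblinding may also occur at the request of the Principal Investigator when all patients have come off study treatment". That sentence sets no condition about follow-up or data lock, and it names no recipients.

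Treatment ends about a year before data collection does. Section 5.3 gives the first dose at about day 90, "followed by doses at days +180 (+/- 10 days), 270 (+/- 10 days) and +365 (+/- 10 days". Section 5.10 states: "Research subjects will be followed until 2 years from the time of transplantation", or until death. The Study Calendar (Section 10) has provider chronic GVHD surveys at months 6, 9, 12, 18 and 24, so two of the five fall after the last dose. Section 5.9 makes one exception: "Patients with malignant disease progression do not require laboratory or clinical follow-up".

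The secondary endpoints in Sections 12.1 and 12.7 include IFS, PFS and OS at 1 and 2 years. They also include overall and NIH moderate-severe chronic GVHD after transplant, with no time point named. On IFS, Section 12.1 says: "IFS is defined as time from randomization to relapse, institution of systemic immune suppression, or death, whichever occurs first". Most of the provider form in Appendix F uses anchored organ scores, such as FEV1 bands, but one item is "Overall GVHD Severity (Opinion of the evaluator". The documents do not say which items feed the NIH moderate-severe endpoint.

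**The concern.** A placebo protects outcome assessment only while assessors do not know the arm. If the option were used as soon as the last patient finished treatment, and codes reached treating physicians or raters, some month-18 and month-24 ratings could be made with knowledge of the arm. So could some decisions to start systemic immune suppression. I found no protocol rule that fixes when such treatment must start, and Section 5.7 leaves tapering to the treating physician. The IFS component therefore rests on judgement.

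At stake are 2-year IFS, and overall and NIH moderate-severe chronic GVHD if ratings after month 12 enter those analyses.

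**Working it through.** **Inputs.** 200 patients at about 100 per year, and one-year steroid-requiring chronic GVHD of 21% and 38% in the earlier rituximab study (Section 12.2). Two-year rates of 31% and 48.5%, and relapse of 34% and 28% with no time point given, from the same study (Section 2.1). Dose 4 at day 365 +/- 10 (Section 5.3). Month-18 and month-24 visits +/- 21 days (Section 10). Assumptions: uniform accrual, time counted from transplant, and the earliest routine trigger, which is the last patient's dose 4. A later request gives smaller numbers.

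1. **The plan's own figure.** 200 / 100 per year = 2.0 years of accrual, as stated.

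2. **Patients short of a visit at the trigger.** With accrual over A months, the share short of month m is (m - 12)/A.
   - Month 24: 12/24 = 50%, or 100 of 200.
   - Month 18: 6/24 = 25%, or 50 of 200.
   - Windows, month 24: from (709 - 375)/730 = 46% (92 patients) to (751 - 355)/730 = 54% (108 patients).
   - Accrual over 18 months (assumption): 12/18 = 67%, or 133. Over 48 months (assumption): 12/48 = 25%, or 50.
   - Simulation with 0%, 30% or 50% of patients stopping treatment early (assumption): the mean month-24 share stays at 49-50%.

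3. **Allowance for progression.** If relapse is 31% (midpoint of 34% and 28%) and all of it comes before these visits (assumption): 100 x 0.69 = 69 and 50 x 0.69 = about 35.

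4. **Patients with 2-year IFS still undetermined.** An earlier event fixes the result, so count only those without one. Taking steroid-requiring chronic GVHD as the only event:
   - Mean of the two groups at year 1: (0.21 + 0.38)/2 = 0.295. At year 2: (0.31 + 0.485)/2 = 0.3975.
   - Events even over year 2: mean (0.295 + 0.3975)/2 = 0.346, so 100 x (1 - 0.346) = 65.4.
   - All year-2 events in months 12-18: 62.8. All in months 18-24: 67.9.
   - Accrual of 18 months: 133.3 x 0.654 = 87. Of 48 months: 50 x 0.654 = 33.
   - Removing 31 relapses without overlap (assumption): 65.4 - 31 = about 34, and fewer after deaths.

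5. **First steroid-requiring events after the trigger (proxy only).** Year-2 events: 200 x (0.3975 - 0.295) = 20.5. An event at month t falls after the trigger with probability (t - 12)/24.
   - Even over year 2: 25%, 5.1 events.
   - All in months 12-18: 12.5%, 2.6 events.
   - All in months 18-24: 37.5%, 7.7 events.

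   The range is about 3 to 8. It is a proxy because steroid-requiring chronic GVHD is a named endpoint only at one year.

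6. **Primary endpoint.** If the last dose 4 is given at day 355, patients within 10 days of month 12 number 10 / (730/200) = 10/3.65 = about 3, each with at most 10 days outstanding. In the early-stopping simulation, on average at most about one patient had not reached month 12.

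**The case against.** **The clause only permits.** Bias needs three steps that the text does not state: prompt use of the option, release of codes to raters or treating physicians, and influence on their judgement. This stands. A reader might infer that the plan will unblind assessors at month 12, and the documents do not say so. But nothing elsewhere delays release or restricts recipients.

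**The 100 of 200 is not the exposure.** This also stands. Under the competing-risks analysis in Section 12.7, a first event before unblinding is already fixed, and progressed patients need no visits. A reader might infer that half the two-year outcomes would be biased, but the figure counts only patients short of a visit. Nor is half an upper limit, since visit windows or faster accrual raise it.

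**Few endpoints are clearly affected.** Two-year IFS is the only dated one that turns on judgement. The chronic GVHD rates are exposed only if ratings after month 12 are used. Section 12.2 guarantees at least one year of follow-up, but that sentence serves the primary endpoint and does not displace the two years in Section 5.10.

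**The arm may show anyway.** Immunoglobulin levels and B-cell subsets are scheduled through month 24 (Section 10, footnote 6). Section 5.8.2 calls for IgG repletion and expects prolonged low levels after B-cell depletion. The documents do not say that these results are masked. If raters see them, later code release gains less. That weakens the benefit, but it is no reason to disclose the codes in full while ratings continue.

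**Conclusion.** The point holds as a low-cost improvement. Section 12.4 allows codes to be released while secondary outcomes that depend on judgement are still being collected. At planned accrual and nominal visit days, about 100 patients would be short of month 24 and about 50 short of month 18, before deaths and progressions. Those with 2-year IFS undetermined number about 65 (63-68 by event timing; 33-87 for accrual of 48 to 18 months) when only steroid-requiring chronic GVHD counts as an event, and fewer after relapse and death.

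These figures rest on uniform accrual, immediate use of the option, and event rates carried over from the earlier rituximab study. The size of any bias cannot be derived from the documents. A reader might infer that the primary result is compromised. The documents do not support that: the last dose and the month-12 assessment fall at the same visit. OS is objective.

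**What to change.** Amend Section 12.4 so that, apart from the existing emergency provision, individual treatment codes go to investigators and GVHD assessors only after the last month-24 visit and data lock. Have an unblinded statistician run the one-year primary analysis and report it at arm level only. With that trigger, the share of patients still to be rated at code release falls from about 50% to 0%.

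The cost is mainly wording. Section 13 allows an abstract before follow-up ends, and an arm-level one-year result serves that purpose. Section 12.5 already has safety endpoints compared between arms, and says of the efficacy analyses: "The interim results will be reported to the DF/HCC DSMB".

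There are two downsides. Patient-level codes, and correlative work by arm that needs them (Section 12.8), would reach investigators up to about a year later. Post-treatment safety and pregnancy reports (Sections 7.4.4 and 7.4.6) would be handled blinded, as they are during treatment. The amendment does not close the possible laboratory route to the arm, so the plan should also state whether raters see B-cell and immunoglobulin results.
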